# 1.4.2. Patient Studies

Three clinical studies (MT-210-A02, CYR-101C01, and MIN-101C03) have been conducted in schizophrenia patients. Two different formulations have been used to date, the SR and the MR. The dose ranges tested in these studies were between 16 and 96 mg for MIN-101 SR (8 mg to 48 mg given twice daily [b.i.d.]) and 32 and 64 mg for MIN-101 MR tablet.

An overview of the clinical studies is presented in Table 2.

Study / Status	Phase	Main Objectives and Design	Drug Doses/Form	Study Population Sex (M/F)	No. of Subjects Enrolled/ Completed
MT-210-A02 Complete	1	Multiple-dose rising study in sequential cohorts DB, PC, Safety/ Tolerability/ PK/ preliminary efficacy	8 to 48 mg b.i.d. SR for 12 days	Schizophrenia patients 11M/1F	12/5
CYR-101C01 Complete	2a	A Multi-center, Inpatient and Ambulatory, Phase 2, DB, Randomized, PC, Proof of Concept Study of CYR-101 in Patients with DSM-5 Schizophrenia	Dose adjustment period 8, 16 and 32 mg SR b.i.d. for two days each. Then fixed dose- period at the optimal dose, maximum of 32 mg b.i.d.; Placebo	Schizophrenia patients 49M/47F	96/30
MIN-101C03 Complete	2b	Multi-center, DB, Randomized, Parallel- group, PC, Study to Evaluate Efficacy, Tolerability and Safety of MIN-101 in Patients with Persistent, Stable, Predominant Negative Symptoms of Schizophrenia, followed by 24 weeks of open-label extension	Placebo, 32 and 64 mg MR for total of 36 weeks.	Schizophrenia patients 137M/107F	244 (randomized) / 165 (completed double-blind phase*) / 88 (completed 36 weeks)

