## 3. GENERAL STATISTICAL CONSIDERATIONS

#### 3.1. SAMPLE SIZE AND POWER

The sample size for this study is based on the assumption of a treatment difference of 3 points in the mean change from Baseline to Week 12 in PANSS negative subscale score based on the Marder NSFS between any MIN-101 dose group and placebo. A standard deviation of 6.5 in the change in PANSS negative subscale score from Baseline is used. Assuming an equal allocation to placebo and each of the 2 MIN-101 doses, 100 patients in each treatment arm are required to detect the treatment difference of 3 points with a power of 90% at an overall 2-sided significance level of

0.05. When adjusted for a rate of about 40% of patients who will not have either Baseline or at least 1 on-treatment efficacy assessments, the required number of patients becomes 167 in each treatment arm. Therefore, the total number of patients enrolled across the 3 treatment arms will be 501.

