#### 3.3.3. Multiple Testing and Comparisons

The study-wise type I error probability for testing the 2 MIN-101 doses versus placebo across both the primary and the key secondary endpoint comparisons will be controlled at the 2-sided 0.05 level using a truncated Hochberg procedure with a truncation parameter of  $\gamma = 1$ .

The primary family of hypotheses and key secondary family hypotheses will be tested using a sequential "gatekeeping" approach with suitable adjustment for multiplicity within the family of primary hypotheses and the family of key secondary hypotheses. A MIN-101 dose versus placebo null hypothesis contrast within the secondary family can only be evaluated when both of the null hypothesis contrasts in the primary family have been rejected.

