## 3.3.4. Missing Data and Outliers

Every effort will be made to obtain required data at each scheduled evaluation from all patients who have been treated. Partial dates will be displayed as captured (without imputation) in subject data listings.

No imputation of data elements will be performed for the primary or key secondary analyses to be submitted to the US Food and Drug Administration (FDA). Pattern-mixture modelling imputation of missing primary and key secondary endpoint data will be performed as part of the primary and key secondary analyses to submit within the European Medicines Agency (EMA) dossier. This approach is detailed in Section 5.2.2.

Sensitivity analyses will be performed to examine the impact of assumptions made for the primary and key secondary analyses as outlined in Section 3.3.4.2.

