#### 3.3.4.1. Multiple Imputation Using Pattern-Mixture Modelling

For the analyses to be submitted within the EMA dossier, multiple imputation using a pattern-mixture modelling approach will be used to impute values for missing primary (12-week NSFS) and key secondary (12-week PSP total score) endpoints data. For the US FDA analysis and dossier, however, the pattern-mixture modelling will serve as a sensitivity analysis.

In pattern-mixture modelling, missing values of each 12-week endpoint measure will be imputed using pattern imputation by treatment group. This method factors in that patients with missing outcome data can have different outcome distributions than those without missing outcome data. This method can accommodate when values of the 12-week endpoint measure are not missing at random (non-ignorable or informative missing data) such that missing values might be systematically different from observed values. Predictors will include changes in the 12-week measure from Baseline using existing data measured at prior post-Baseline visits, and additional factors of region, age grouping using median, gender, race, body mass index (BMI) grouping (≤30 kg/m², >30 kg/m²), and treatment group. A total of 30 imputed datasets will be generated, analysis will be performed on multiple imputed datasets, and the results will be combined.

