#### 5.2.2. Primary Efficacy Analysis

As noted in Section 3.3.4, no imputation of data elements will be performed for the primary analysis to be submitted to the US FDA. Pattern-mixture modelling imputation of missing primary endpoint data will be performed before conducting the primary analysis to submit within the EMA dossier. In both approaches, the estimand and analytic approach of using MMRM to evaluate the potential treatment effects is the same, but the data used to analyze the estimand is different between the US FDA and EMA dossiers.

The PANSS Marder NSFS scores and change from Baseline will be summarized by treatment group and study visit. In addition, the trend in change from Baseline in Marder NSFS scores over the series of visit assessments will be presented graphically.

Change from Baseline to Week 12 in the PANSS Marder NSFS score will be analyzed using a MMRM with fixed effects for treatment group (MIN-101 64 mg, MIN-101 32 mg, and placebo), region, visit, and treatment-by-visit interaction, a random effect for patient within treatment group, and Baseline NSFS as covariate. An unstructured covariance matrix will be used to model the covariance of within-patient scores. The Kenward-Roger approximation will be used to estimate denominator degrees of freedom. Comparison against placebo will be performed with the MIN-101 64 mg and 32 mg doses.

The hypotheses can be expressed as follows:

```
Null Hypothesis (H_0): \muMIN-101 64 mg - \muControl = 0 and \muMIN-101 32 mg - \muControl = 0
```

Alternative Hypothesis (Ha):  $\mu$ MIN-101 64 mg -  $\mu$ Control  $\neq$  0 or  $\mu$ MIN-101 32 mg -  $\mu$ Control  $\neq$  0

where  $\mu$ MIN-101 64 mg and  $\mu$ MIN-101 32 mg refer to the mean change from Baseline to week 12 in the PANSS Marder NSFS score at each of the 2 experimental doses, and  $\mu$ Control refers to the mean change from Baseline to week 12 in the PANSS Marder NSFS score in the placebo arm.

As described in Section 3.3.3.1, the adjustment for multiplicity within the family of primary hypotheses will utilize the truncated Hochberg procedure for the purpose of reporting results. This procedure will allow the null hypothesis of no treatment difference for both the 64 mg and 32 mg doses versus placebo to be rejected if largest p-value of comparing either of these 2 doses versus placebo is at or below 0.05. Otherwise, the lowest of these 2 p-values must be at or below 0.025 reject the null hypothesis for the representative dose.

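### Thirty imputations with no stated seed leave the EMA primary p-value imprecise when it falls near a cut-off; use about 1000 and fix the seed

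*SAP*

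**What the plan says.** SAP 3.3.4.1 describes pattern-mixture imputation by treatment group and ends by fixing the number: "A total of 30 imputed datasets will be generated", each to be analysed and the results pooled. Its predictors include "changes in the 12-week measure from Baseline using existing data measured at prior post-Baseline visits", together with region, age group, gender, race, BMI group and treatment.

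For the FDA this is a sensitivity analysis. For the EMA it is confirmatory: SAP 3.3.4 says that "Pattern-mixture modelling imputation of missing primary and key secondary endpoint data will be performed as part of the primary and key secondary analyses" in that dossier, and SAP 5.2.2 repeats that "Pattern-mixture modelling imputation of missing primary endpoint data will be performed before conducting the primary analysis to submit within the EMA dossier".

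Error across the two doses and the two endpoints "will be controlled at the 2-sided 0.05 level using a truncated Hochberg procedure" (SAP 3.3.3). Both doses succeed if the larger p is at most 0.05; otherwise the smaller must be at most 0.025 (SAP 3.3.3.1). PSP is tested only if both primary comparisons succeed (SAP 3.3.3.2).

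Neither document states a seed, a tolerance for Monte Carlo error, or a reason for choosing 30.

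**The concern.** A p-value pooled over a finite number of imputations has two sources of randomness: the trial data, and the random draws that fill the gaps. The second should be negligible when the result is compared with a fixed threshold. With a substantial share of Week 12 values imputed, 30 draws may not achieve that. Two analysts following the SAP exactly, on the same locked data, could then land on opposite sides of 0.05 or 0.025. Because of the gate, one such flip in the larger primary p would also decide whether either PSP comparison can be tested. With no seed written down, the choice of seed could be questioned afterwards.

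**Working it through.** **The plan's own figure.** n per arm = 2(1.960 + 1.282)² × 6.5²/3² = 98.7, so 99, or 100 with the t distribution. Power at 100 per arm is 0.904. Then 100/0.6 = 166.7, so 167 per arm and 501 in total. SAP 3.1 reproduces, at an unadjusted two-sided 0.05.

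**Inputs.**
- M = 30 (SAP 3.3.4.1).
- Missing Week 12 data: 32-40%, an assumption. The lower value is Phase 2b non-completion, from "244 (randomized) / 165 (completed double-blind phase" in Protocol 1.4.2: 1 − 165/244 = 32.4%. The upper value borrows the sample-size allowance in SAP 3.1.
- Fraction of missing information λ: 0.2-0.4, an assumption. It is usually below the missing fraction because earlier visits predict Week 12.

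**Formula.** Hold the data fixed and scale the contrast so that its total variance with unlimited imputations is 1: within-imputation 1 − λ, between-imputation λ. With M imputations:
- the pooled estimate varies across seeds with variance λ/M;
- the estimated between-imputation variance is B = λ·χ²(M−1)/(M−1);
- Rubin's total variance is T = (1 − λ) + (1 + 1/M)B;
- the test statistic is the estimate divided by √T, referred to t with Barnard-Rubin degrees of freedom.

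The seed SD of the statistic is approximately √[λ/M + z²λ²/(2(M−1))]. At a converged p of 0.04, z = 2.054:
- λ = 0.2: √(0.00667 + 0.00291) = 0.098.
- λ = 0.4: √(0.01333 + 0.01164) = 0.158.

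**Results at a converged p of 0.04** (200,000 draws per cell):

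| λ | SD of statistic, M = 30 | 95% seed range of p, M = 30 | Seeds with p > 0.05, M = 30 | 95% seed range of p, M = 1000 |
|---|---|---|---|---|
| 0.2 | 0.098 | 0.025-0.064 | 19% | 0.037-0.043 |
| 0.3 | 0.129 | 0.022-0.073 | 27% | 0.036-0.044 |
| 0.4 | 0.158 | 0.019-0.083 | 32% | 0.035-0.045 |

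The reverse also occurs: at a converged p of 0.06, roughly a fifth of seeds give 0.05 or less. At the 0.025 step, with a converged p of 0.02, the reported p exceeds 0.025 for 23%, 32% and 37% of seeds at λ = 0.2, 0.32 and 0.4.

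**Cross-check.** Trials were simulated with 167 per arm, four visits, monotone dropout and by-arm regression imputation, and each was re-imputed 120 times with M = 30. With 32% missing (λ = 0.17 and 0.29, reference p 0.040), p ran from 0.018 to 0.067 and from 0.019 to 0.105. With 40% missing (λ = 0.21 and 0.38, reference p 0.035 and 0.044), it ran from 0.022 to 0.060 and from 0.019 to 0.094. The reference values rest on 600 imputations and carry some noise of their own.

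**Where the trial might land.** With SD 6.5 and 100 evaluable per arm, SE = 6.5 × √(2/100) = 0.919.
- 3 points (design): z = 3.26, p about 0.001. No seed matters.
- 1.97 points (Phase 2b, 64 mg; Protocol 1.4.2.2): z = 2.14, p about 0.03.
- 1.54 points (Phase 2b, 32 mg): z = 1.68, p about 0.09.

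**The case against.** **The 40% is not a Week 12 missing rate.** A reader might infer that the trial plans for 40% missing Week 12 data. SAP 3.1 words it as "a rate of about 40% of patients who will not have either Baseline or at least 1 on-treatment efficacy assessments", which is a sample-size allowance. This stands, so the figure is used here only as the upper end of an assumed range. The Phase 2b rate of 32% leads to the same conclusion.

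**The percentages are conditional on a borderline p.** This also stands. Over repeated trials, for a single contrast, the decision at 0.05 with 30 imputations differs from the unlimited-imputation decision in 1.4-2.4% of trials at the design effect, 3-5% at the Phase 2b effects and 0.9-1.4% under the null. Type I error stays at 0.048-0.049 and power falls by 0.2-1.1 points. A reader might infer bias or inflated error; the calculation shows neither.

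**A borderline p may be unlikely.** The p-values of 0.03 and 0.09 depend on the plan's SD. Phase 2b reported p of 0.0240 and 0.0036 for those effects, which implies an SE near 0.68 (1.54/2.26 and 1.97/2.91). Scaled by √(244/501), that is 0.475, giving z of 3.2 and 4.1, outside the sensitive range. So the closeness is an illustration under the SAP's own assumption and not a forecast.

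**The model is simplified.** The check uses Rubin pooling of one contrast, and the simulation used regression imputation. The SAP plans pattern-mixture imputation followed by MMRM. The principle carries over; the exact percentages need not.

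**There are safeguards.** SAP section 5 requires verification by independent programming, which might expose a seed discrepancy. SAP 3.3.4.2 adds observed-data, LOCF and placebo-mean analyses for the EMA, and the FDA primary analysis uses no imputation. None of these fixes a seed or reduces the noise in the EMA primary p-value.

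**Conclusion.** The point holds in a limited form. Under the assumed missingness and λ of 0.2-0.4, 30 imputations leave seed noise of about 0.10-0.16 in the EMA test statistic. That is enough to change the conclusion for about one seed in five to one in three if the converged p is 0.04, with similar exposure at the 0.025 step and hence at the PSP gate. For the 0.05 cut-off, flips become rare once the converged p is outside roughly 0.02-0.10.

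A reader might go further and call the EMA primary p-value seed-dependent in general. The plan's figures do not support that: at the effect for which the trial is powered, the seed is irrelevant. This is a gap in reproducibility and precision that is cheap to close, and it does not undermine the analysis.

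**What to change.** In SAP 3.3.4.1, before unblinding of the double-blind phase:
- replace 30 with about 1000 imputed data sets;
- state the random seed;
- report the Monte Carlo error of the pooled estimate and of the p-value.

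The number and the seed do different jobs. A stated seed makes the result repeatable and rules out choosing one later, but does not make the p-value more precise. More imputations do. Even 1000 cannot protect a p very close to the cut-off: at a converged p of 0.045 and λ = 0.4, the distance to the threshold is 2.005 − 1.960 = 0.045 against a seed SD of about 0.027, so about 5% of seeds would still cross. At 300 imputations, the share at the same p is already 15% with λ = 0.32, so 300 is a weaker choice. Hence the request to report the Monte Carlo error.

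The cost is a short text change and a little computing time. The design, estimand, imputation model and patients are unaffected.

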#### 3.3.4.2. Sensitivity Analysis of the Primary Endpoint

For the FDA analysis and dossier, three approaches will be used as sensitivity analyses to explore the potential impact of missing data on the primary and key secondary endpoint comparisons: Multiple imputation using pattern-mixture modelling (Section 3.3.4.1), last-observation-carried-forward (LOCF), and placebo mean imputation.

For the EMA analysis and dossier, a slightly different approach will be used for sensitivity analyses. The first will explore the difference between the use of only observed primary and key

secondary endpoint data, as well as the approaches of last-observation-carried-forward (LOCF) and placebo mean imputation.

## 3.3.4.2.1. Last-Observation-Carried-Forward (LOCF)

The LOCF approach to impute values for missing primary (12-week NSFS) and key secondary (12-week PSP total score) endpoint data will be implemented as follows:

Missing values of the 12-week endpoint measure will be imputed to the last post-Baseline endpoint measure (of those measured at the prior post-Baseline visits), thus treating the evaluations of the endpoint measures as generally stable over time. Note that this assumption may give overly optimistic results if withdrawal in active arm(s) occurs earlier than in the control arm, such as due to improvement of the patient's condition or adverse events.

### 3.3.4.2.2. Placebo Mean Imputation

The Placebo Mean Imputation approach to impute values for missing primary (12-week NSFS) and key secondary (12-week PSP total score) endpoint data will be implemented as follows:

Missing values of the 12-week endpoint measure will be imputed with the mean of available 12-week endpoint measures within placebo-treated patients. Note that this method can be influenced by the data from patients completing 12 weeks of the study, yet the outcomes of patients completing the study may not represent the outcomes of patients not completing the study, such as if patients with deterioration of their condition or adverse events were to drop out prematurely.

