Sensitivity analyses of the primary endpoint will also be performed and will be detailed further in the SAP. These may include an ANCOVA model with factors for treatment and region and Baseline NSFS as a covariate. In this analysis, subjects without a NSFS at Week 12 will have an earlier postbaseline score imputed using the LOCF method. Other sensitivity analyses may also be performed to investigate the robustness of treatment estimates to the observed pattern of, and/or reason for, early withdrawals. Additional details will be provided in the SAP, including pre-specified sensitivity analyses under "non-ignorable" missing data mechanisms to assess the potential impact of the incorrect missing data assumption made for the primary analysis.

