## 5.2.1. Primary Estimand

The primary estimand, the main clinical quantity of interest to be estimated in the study, is defined by the following components:

**Population**: Stable patients with schizophrenia with a predefined minimum PANSS negative symptom score before randomization.

**Endpoint**: Change in the PANSS Marder NSFS from Baseline to the end of Week 12.

The NSFS consists of the sum of the ratings (on a scale of 1-7, from least to highest severity of psychopathology) across the PANSS items N1, N2, N3, N4, N6, G7, and G16. Thus, each assessment is a number between 7 and 49.

N1. Blunted affect

N2. Emotional withdrawal

N3. Poor rapport

N4. Passive/apathetic social withdrawal

N6. Lack of spontaneity

G7. Motor retardation

G16. Active social avoidance

**Measure of Intervention**: The effect of the initially randomized treatment that would have been observed had all patients remained on their treatment throughout the double-blind phase.

**Intercurrent events**: Early study discontinuation for any reason.

**Summary measure**: Difference in treatment means.

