Three approaches will be used to assess the sensitivity of the primary endpoint to patterns of early withdrawals or missing data as described in Section 3.3.4.2. The sensitivity analyses will implement the same analytic approach using MMRM to evaluate potential treatment effects.

Finally, a cumulative distribution function for the change from Baseline to Week 12 in the PANSS Marder NSFS score will be presented.

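### The pattern-mixture imputation in SAP 3.3.4.1 states no identifying assumption, and the placebo mean fill in 3.3.4.2.2 leaves its scope open and treats a constant as observed data

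*SAP*

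**What the plan says.** SAP 3.3.4.1 describes multiple imputation by pattern-mixture modelling for missing Week 12 NSFS and PSP scores, and says the method can handle informative missingness. On the mechanics it says that "missing values of each 12-week endpoint measure will be imputed using pattern imputation by treatment group". On inputs: "Predictors will include changes in the 12-week measure from Baseline using existing data measured at prior post-Baseline visits". It adds region, age group, gender, race, BMI group and treatment group, and 30 imputed datasets. Nothing further is specified.

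The role of this imputation differs by dossier. SAP 5.2.2 says: "Pattern-mixture modelling imputation of missing primary endpoint data will be performed before conducting the primary analysis to submit within the EMA dossier". For the FDA it is a sensitivity analysis, beside LOCF and placebo mean imputation (SAP 3.3.4.2). The EMA sensitivity set is observed data only, "as well as the approaches of last-observation-carried-forward (LOCF) and placebo mean imputation".

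SAP 3.3.4.2.2 defines the placebo fill: "Missing values of the 12-week endpoint measure will be imputed with the mean of available 12-week endpoint measures within placebo-treated patients". It warns that completers may not represent dropouts. It does not say which arms receive the value, adds no random draw, and does not mention the standard error. SAP 5.2.2 then says: "The sensitivity analyses will implement the same analytic approach using MMRM to evaluate potential treatment effects". SAP 5.2.5 repeats this for PSP.

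The estimand in SAP 5.2.1 is hypothetical: "The effect of the initially randomized treatment that would have been observed had all patients remained on their treatment throughout the double-blind phase". Protocol 10.5.1 committed the SAP to pre-specified analyses under non-ignorable mechanisms, "to assess the potential impact of the incorrect missing data assumption made for the primary analysis".

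**The concern.** A pattern-mixture model is not identified by the data. Something must be assumed about how unobserved outcomes in each dropout pattern relate to observed ones. Without that statement two programmers could not reproduce the same analysis, and a reader cannot tell whether it departs from missing at random (MAR) at all. Imputing within arm from earlier visits and covariates, with nothing more, would be ordinary MAR imputation. It would then share the assumption of the observed-data MMRM instead of testing it.

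This weighs most in the EMA dossier. There the unspecified method is primary, and the departures left to challenge it are LOCF and the placebo fill. Each is a single scenario, and neither can be graded to find where the conclusion changes.

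The smaller issue is that a constant entered as observed data gives the model the wrong precision when dropout differs by arm. The strictness of that check then depends on which arm loses more patients.

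**Working it through.** **The plan's own figures.** With a difference of 3, SD 6.5, 90% power and two-sided 0.05 (SAP 3.1), n = 2 × (1.960 + 1.282)² × 6.5² / 3² = 98.7, so 99 per arm against 100 stated (power at 100 is 90.4%). Then 100 / 0.6 = 166.7, giving 167 per arm and 501 in total. These reproduce.

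**Missingness.** The 40% in SAP 3.1 concerns patients without a Baseline or any on-treatment assessment, which is not Week 12 missingness. I use Phase 2b non-completion instead (protocol 1.4.2, Table 2): (244 − 165) / 244 = 79 / 244 = 32.4%. No per-arm dropout is given, so the splits below are assumptions centred near 32%.

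**Pattern-mixture analysis.** Suppose MIN-101 dropouts do 3 points worse after leaving than their observed visits predict, with a difference of 3 otherwise. The true difference is 3 − 0.324 × 3 = 2.03. In simulation (three arms of 167; Weeks 2, 4, 8 and 12; Week 12 change SD 6.5; assumed baseline SD 4.5, baseline-change correlation −0.35 and visit correlations 0.55 to 0.80):

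- Primary MMRM: 3.00.
- Within-arm imputation, one literal reading of 3.3.4.1: 3.00.
- The same imputation with a 3-point delta: 2.03.
- Placebo mean fill: 2.03, in a separate Week 12 ANCOVA simulation. By formula it is (1 − 0.324) × 3 = 2.03.

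The fill recovers this case because a 3-point shift at a 3-point effect means dropouts lose all benefit, which is what the fill assumes.

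**Tipping point.** With an imputation SE of 0.765, the estimate must stay above 1.96 × 0.765 = 1.50. A shift δ in MIN-101 dropouts lowers it by 0.324δ.

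- At the planned effect of 3: (3 − 1.50) / 0.324 = 4.6 points (simulated: about 4.5).
- At the Phase 2b 64 mg effect of 1.97 (protocol 1.4.2.2): (1.97 − 1.50) / 0.324 = 1.5 points (simulated: about 1.5).

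No analysis in the SAP would show these numbers.

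**Standard error of the fill.** Let q_a and q_p be the fractions observed in MIN-101 (same in both dose arms) and placebo, with dropout completely at random and all arms filled. The estimate is q_a × (mean_a − mean_p). In units of σ²/n:

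- True variance: q_a + q_a²/q_p.
- Variance reported by a model pooling three arms, under the null: 2(2q_a + q_p)/3.

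Setting them equal with r = q_a/q_p gives 3r² − r − 2 = 0, whose only positive root is r = 1, that is, equal dropout.

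| Dropout MIN-101 / placebo | True | Reported | SE ratio | Type I error, formula | MMRM simulation |
|---|---|---|---|---|---|
| equal, 32.4% | 1.352 | 1.352 | 1.00 | 5.0% | 5.1% |
| 30% / 36% | 1.466 | 1.360 | 1.038 | 5.9% | 5.7% |
| 28% / 40% | 1.584 | 1.360 | 1.079 | 6.9% | 6.9% |
| 34% / 28% | 1.265 | 1.360 | 0.964 | 4.2% | 4.1% |
| 36% / 24% | 1.179 | 1.360 | 0.931 | 3.5% | 3.7% |

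The simulation used 8,000 null trials per split (Monte Carlo SE under 0.3 points). If only the MIN-101 arms are filled, simulated type I error is 2.0% to 2.6% across these splits.

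If half of the non-completers supply a Week 12 score (an assumption), 28/40 becomes 14/20 and the formula gives 5.7%; 30/36 becomes 15/18 and gives 5.35%. ANCOVA simulation gave 5.8% and 5.2%.

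**The case against.** A reader might infer that the EMA primary imputation is in effect MAR. The documents do not establish that. SAP 3.3.4.1 says patients with missing data can have different outcome distributions. It also lists treatment group as a predictor while imputing by treatment group, so a genuine pattern model may be intended. The 3.00 above describes one reading, not the SAP's method. What stands is that the method is underspecified.

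A reader might also infer that nothing in the SAP departs from MAR. That is wrong. LOCF and the placebo fill both do, and the fill penalises MIN-101 dropouts in a useful way, so protocol 10.5.1 is partly met. What stands is that each tests one point only.

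On the standard error, the defence is largely right about size. The effect is under 1 percentage point at a 6-point gap, and 6.9% needs a 12-point gap that no document reports. Earlier relapse rates (25% placebo, 13% MIN-101 in CYR-101C01, protocol 1.4.2.2) suggest a direction but are not dropout rates for this trial. Protocol 8.1.3.4 and 9.2 also seek Week 12 assessments from early terminators. SAP Table 1 includes a termination visit in its Week 12 row, although a footnote appears to tie that row to safety tables. Any such scores shrink the effect.

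Finally, a sensitivity test cannot rescue a failed primary, so inflated trial type I error is not a supportable reading.

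**Conclusion.** The concern holds as a specification gap. SAP 3.3.4.1 does not state what makes its imputation non-ignorable, so it cannot be reproduced or confirmed as the analysis the protocol promised. This matters most where it is the EMA primary. The fixed scenarios around it do not locate the tipping point, which would be only about 1.5 points at the Phase 2b 64 mg effect under the assumptions above.

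The placebo fill is a secondary matter. It is a reasonable departure from MAR whose scope is unstated. Its standard error is wrong in either direction when dropout is unequal, by roughly −7% to +8% at 12-point gaps. That result assumes dropout completely at random, equal variances, equal dropout in the two dose arms, and filling of every arm. At equal dropout the standard error is right. The FDA primary MMRM is untouched.

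**What to change.** 1. In SAP 3.3.4.1, define the patterns and state the identifying assumption. Add a delta-adjusted tipping-point analysis for NSFS and PSP on the 30 imputations already planned, in both dossiers.
2. Replace the constant fill with placebo-based multiple imputation: missing MIN-101 values drawn from the placebo model given the patient's own baseline and visits, placebo under MAR, combined by Rubin's rules. Label it conservative and as departing from the hypothetical estimand in 5.2.1. If the constant fill is kept, say which arms it applies to and label it descriptive.

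The cost is some SAP text and programming, and less favourable sensitivity p-values. In simulation, placebo-based imputation had type I error of 1.4% to 2.4%. At a true difference of 3 it gave an estimate of 2.53 and power of 96%, against 98% for the primary MMRM. It answers a different question from the estimand, so it supplements the tipping point and does not replace it.

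Adding the Baseline score to the imputation predictors is optional; the simulated SE moved only from 0.774 to 0.765.
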